**Study 111-301 Statistical Analysis Plan****15 SAFETY EVALUATIONS**

The safety population will be used for all summaries where assessments/events are reported by treatment group.

Summary tables will include all safety events up to 30 days following treatment discontinuation. PI [REDACTED]

Safety will be assessed by examining the incidence, severity (determined using the Common Terminology Criteria for Adverse Events (CTCAE) version 4), and relationship to study drug of all treatment-emergent adverse events (TEAEs) reported during the study period. In addition, changes from baseline in clinical laboratory results and vital signs will be assessed.

15.1 Adverse Events

Adverse events (AEs) will be coded in accordance with Medical Dictionary for Regulatory Activities (MedDRA) Version 22. MedDRA coding will be performed prior to database lock. Coding of the severity of adverse events is performed by the investigators using NCI CTCAE version 4, where events are coded from CTCAE Grade 1 to Grade 5.

Only treatment-emergent adverse events (TEAEs) defined as any adverse event that newly appeared, increased in frequency, or worsened in severity following initiation of study drug administration are reported by the investigators and consequently are included in the summary tables.

In the event that the start date of an AE is incomplete or missing, conservative imputation rules are applied so that where there is uncertainty, the event is considered treatment emergent. Similarly the AE end dates are imputed in a conservative manner to a maximum length (Section 5.5.1).

15.1.1 Treatment-Emergent Adverse Events

Treatment-emergent adverse events (TEAEs) will be summarized by treatment group. In summaries by system organ class (SOC) and/or preferred term (PT), subjects with more than one AE of the same SOC or PT will be counted once within that SOC/PT. The tables are ordered by the frequency of the highest reporting level (SOC or PT) in the table within the active treatment group.

The following summary tables will be provided:

- Overview of the incidence of adverse events

	Study 111-301 Statistical Analysis Plan
---	--

- Incidence and exposure-adjusted event rates of TEAEs by system organ class (SOC), preferred term (PT) and CTCAE grade
- Incidence of TEAEs by system organ class (SOC), preferred term (PT) and highest CTCAE grade
- Incidence and exposure-adjusted event rates of TEAEs by PT
- Incidence and exposure-adjusted event rates of TEAEs by SOC
- Incidence and exposure-adjusted event rates of drug-related TEAEs by SOC, PT and CTCAE grade
- Incidence of serious adverse events (SAEs) by SOC and PT
- Incidence of TEAEs leading to study or study drug discontinuation by PT
- Incidence of TEAEs leading to study drug interruption by PT
- Incidence of TEAEs leading to study drug dose reduction by PT
- Incidence and exposure-adjusted event rates of achondroplasia-related TEAEs by SOC and PT*

* Achondroplasia-related TEAE's will be identified using the PT's identified for achondroplasia-related medical history (see Section 10). In addition, all AEs will be reviewed prior to database lock and the list updated as required.

PI [redacted]

[redacted]

[redacted]

[redacted]

[redacted]

[redacted]

[redacted]

[redacted]

15.1.2 Events of Interest

Events of interest (EOI) will be summarized by PT and treatment group.

The following are identified as events of interest:

Injection site reactions (ISR)

Study 111-301 Statistical Analysis Plan

- TEAEs with a MedDRA High Level Term (HLT) of “Injection site reaction”.

Hypotension

- TEAEs with PT: Blood pressure ambulatory decreased, Blood pressure decreased, Blood pressure diastolic decreased, Blood pressure orthostatic decreased, Blood pressure systolic decreased, Blood pressure systolic inspiratory decreased, Diastolic hypotension, Hypotension, Orthostatic hypotension.

Heart rate change

- TEAEs with a PT: Atrial tachycardia, Postural orthostatic tachycardia syndrome, Rebound tachycardia, Sinus tachycardia, Supraventricular tachycardia, Tachycardia, Tachycardia paroxysmal, Ventricular tachycardia, Bradycardia.

Hypersensitivity SMQ

- TEAEs with a PT included in the MedDRA hypersensitivity SMQ

Algorithmic Anaphylaxis SMQ (with sponsor-defined time restrictions)

- TEAEs with a PT included in the MedDRA anaphylactic reaction SMQ, with an additional time restriction: a narrow scope PT at any time, or two broad scope PTs from different classes where both PTs are within 24 hours of the same dose.

Fractures

- TEAEs with a MedDRA HLT: Fractures NEC, Limb fractures, Pelvic fractures, Skull and face fractures, Spinal column fractures, thoracic cage fractures non-spinal

Slipped Capital Femoral Epiphysis (SCFE)

- TEAEs with a PT: Epiphyseal disorder, Epiphyseal injury

Avascular necrosis and osteonecrosis

- TEAEs with a PT: Osteonecrosis, Osteonecrosis of jaw, Osteonecrosis of external auditory canal, Necrosis ischaemic

[figure not shown]
Events of interest will be summarized as follows:

- Incidence and exposure-adjusted event rates of injection site reaction events by PT
- Incidence and exposure-adjusted event rates of injection site reaction events by PT and duration of ISR (≤ 15 min, > 15 min and ≤ 60 min, > 60 min and ≤ 120 min, > 120 min and ≤ 24 hours, > 24 hours)
- Incidence and exposure-adjusted event rates of hypotension by PT
- Incidence and exposure-adjusted event rates of heart rate change events by PT
- Incidence and exposure-adjusted event rates of hypersensitivity (SMQ)

	Study 111-301 Statistical Analysis Plan
---	--

- Profile of injection site reaction events
- Profile of hypotension
- Profile of heart rate change events

Profile summaries include: highest CTCAE grade, number of events per subject, time from first dose to first event onset, duration of events (days), action taken with study drug, outcome of events.

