7.2.2 Study 111-202

Study 111-202 was a Phase 2, open-label, sequential cohort, dose escalation study that assesses daily SC administration of BMN 111 in pediatric subjects with ACH. The primary objective of Study 111-202 was to evaluate the safety and tolerability of BMN 111 administered for 6 months and up to 24 months; the secondary objectives were to determine change from baseline in annualized growth velocity (AGV), growth parameters, body proportions, and evaluate the dose-exposure and PK profiles of BMN 111 in children with ACH.

Analysis of safety data from the 6-month initial phase of Study 111-202 showed that treatment with BMN 111 for 6 months at dose cohorts of 2.5, 7.5, 15, and 30 µg/kg (Cohorts 1 to 4, respectively) was generally well tolerated. The most common AEs were mild injection site reactions, pyrexia, asymptomatic hypotension, headache, and nasopharyngitis. For a detailed summary of risks, please refer to the current version of the Investigator's Brochure supplied by BioMarin.

Analysis of efficacy data from the 6-month initial phase of Study 111-202 demonstrated that the mean (standard deviation) change from baseline AGV when BMN 111 is administered at 2.5, 7.5, 15, and 30 µg/kg subcutaneously daily for 6 months is -0.37 (1.592), 1.28 (1.439), 2.01 (1.999), and 2.08 (2.137) cm/year, respectively. Thus, a positive dose-dependent response was observed in change from baseline AGV at doses ranging from 2.5-15 µg/kg daily.

In regards to 12-month data, subjects in Cohort 3 completed 12 months on a stable daily dose of 15 µg/kg and positive change from baseline in AGV was observed in subjects in Cohort 3. Subjects treated with 30 µg/kg daily also showed similar improvement in mean AGV after 6 months and their mean changes from baseline in AGV were similar to subjects treated with 15 µg/kg daily. Safety data for the 30 µg/kg daily dose was also similar to the 15 µg/kg daily dose. Thus, no clinically significant difference could be identified between the 15 µg/kg and 30 µg/kg daily dose in the Phase 2, 6-month safety and efficacy data.

Single-dose PK data from Day 1 showed BMN 111 was rapidly absorbed (median T_{max} between 5.00 and 16.0 minutes) and rapidly cleared from plasma (mean $t_{1/2}$ ranging from 24.4 to 27.0 minutes).

	Study 111-301 Amendment 4	Page 38
---	---------------------------	---------

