7.5.2 Summary of Risks from Clinical Studies

7.5.2.1 Study 111-101

Based on review of the first-in-human Phase 1 study of BMN 111 in healthy adult volunteers, Study 111-101, BMN 111 administered SC daily was well tolerated with doses ranging from 0.5 µg/kg to 15 µg/kg. All AEs were of mild severity, and no SAEs were reported. The most common AE was mild, transient, self-limited orthostatic hypotension, of which the majority of cases were asymptomatic and observed only upon assumption of an upright posture following recumbence. No dose-limiting toxicities were identified outside of these CV findings.

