10.3.1.2 Adverse Events Occurring Secondary to Other Events

In general, AEs occurring secondary to other events (eg, cascade events) should be identified by their primary cause. For example, if severe diarrhea is known to have resulted in dehydration, it is sufficient to record only diarrhea as an AE or SAE on the eCRF. However, medically important events that may be linked and/or separated in time should be recorded as independent events on the eCRF. For example, if severe hemorrhage leads to renal failure, both events should be recorded separately on the eCRF.

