10.3.1.4 Hypotension

If an asymptomatic drop in blood pressure meets the protocol definition of AE per clinical judgment of the reporter, report the event as “blood pressure decreased.” If the drop in blood pressure is associated with signs or symptoms, complete the symptomatic hypotension eCRF and use the following guidance to report the corresponding AE eCRF: If a unifying diagnosis is available to explain the event of hypotension, report the diagnosis as an AE and capture signs and symptoms on the symptomatic hypotension eCRF page. If no other unifying diagnosis is available, report “hypotension” as the event and capture signs and symptoms on the symptomatic hypotension eCRF page.

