14.4 Safety Analysis

All randomized subjects who receive at least one dose of double-blinded BMN 111 or placebo in this study will be included in the safety analysis. The safety analysis will be performed on safety population as defined in Section 14.7.2 and will be considered descriptive.

All AEs will be coded using the most current version of MedDRA will be used by the Sponsor to assign system organ class and preferred term classification to events and diseases, based on the original terms entered on the CRF.

All AEs will be coded using MedDRA. The incidence of AEs will be summarized by system organ class, preferred term, relationship to study treatment (as assessed by investigator), and severity. All AEs, including SAEs and AEs that lead to permanent discontinuation from the study and from the study treatment, will be listed. Hypersensitivity reactions and symptomatic hypotension are of interest, and the percentage of subjects who report these AEs will be presented. Hypersensitivity reactions will be defined in the SAP.

Clinical laboratory data will be summarized by the type of laboratory test. For each clinical laboratory test, descriptive statistics will be provided on baseline as well as all subsequent visits.

Descriptive statistics for other safety endpoints such as vital signs, ECG results, X-ray and DXA assessments of bone morphology and quality, clinical hip assessment, CBCL, anti-BMN 111 immunogenicity assessments, and bone metabolism biomarkers, will also be provided. Detailed statistical methods will be provided in the SAP. All other safety measures including laboratory tests, vital signs, ECG, X-ray and DXA assessments, clinical hip assessment, and anti-BMN 111 immunogenicity (discussed in the next section) will be summarized descriptively by group, listings will be provided for these safety endpoints.

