15.1.3 Injection Site Reaction Symptoms

Injection site reactions (ISRs) associated with single symptoms are recorded on the AE page (as a single symptom). ISR's with multiple symptoms are recorded as an AE of "Injection Site Reaction" on the AE page and the associated individual symptoms are recorded on the ISR symptom page.

In order to describe all ISR symptoms recorded, summaries will be based on the data collected on the ISR Symptoms page and also those single symptoms recorded as an adverse event.

Incidence and exposure-adjusted event rates of ISR Symptoms will be summarized by PT and treatment group.

ISR Symptoms will be listed.

Study 111-301 Statistical Analysis Plan

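### No visible SAP output uses the symptomatic hypotension eCRF, so the hypotension profile mixes asymptomatic with symptomatic events and the symptomatic percentage in protocol 14.4 may be incomplete

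*SAP*

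**What the plan says.** Protocol 14.4 (Safety Analysis) states: "Hypersensitivity reactions and symptomatic hypotension are of interest, and the percentage of subjects who report these AEs will be presented".

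Protocol 10.3.1.4 (Hypotension) sets the reporting rules. The asymptomatic rule begins "If an asymptomatic drop in blood pressure meets the protocol definition of AE per clinical judgment of the reporter", and the AE term is then 'blood pressure decreased'. Any drop with signs or symptoms calls for the symptomatic hypotension eCRF. If a unifying diagnosis explains the drop, the site is told to "report the diagnosis as an AE and capture signs and symptoms on the symptomatic hypotension eCRF page". If there is none, the AE term is 'hypotension', again with the form.

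Protocol 10.3.1.2 adds that secondary events are generally recorded under their primary cause, with an exception: "medically important events that may be linked and/or separated in time should be recorded as independent events on the eCRF".

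SAP 15.1.2 (Events of Interest) defines hypotension by nine MedDRA preferred terms (PTs), starting "TEAEs with PT: Blood pressure ambulatory decreased, Blood pressure decreased, Blood pressure diastolic decreased". The other six include 'Hypotension', 'Orthostatic hypotension' and 'Diastolic hypotension'. Two outputs follow: incidence and exposure-adjusted event rates by PT, and a 'Profile of hypotension' covering highest grade, events per subject, time to first onset, duration, action taken and outcome.

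For injection site reactions, by contrast, SAP 15.1.3 does draw on the symptom page: "summaries will be based on the data collected on the ISR Symptoms page and also those single symptoms recorded as an adverse event".

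**The concern.** Protocol 7.5.2.2 names hypotension as an identified risk of BMN 111. Earlier experience suggests that many recorded events carry no symptoms. In healthy adults (Study 111-101) orthostatic hypotension was the most common AE, "of which the majority of cases were asymptomatic and observed only upon assumption of an upright posture". In children (Study 111-202), "The most common AEs were mild injection site reactions, pyrexia, asymptomatic hypotension, headache, and nasopharyngitis".

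The reader of the safety section will want to know how often a child had a drop with symptoms, and how severe and long those events were. The protocol provides a form that marks exactly those events. If the form feeds no output, the severity, duration and action-taken summary may mainly describe asymptomatic readings, and some symptomatic events may not be recognisable as hypotension at all.

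**Working it through.** The plan states no figure on this point, so there is none to reproduce. The check sets the reporting rules beside the outputs, then sizes the gaps under stated assumptions.

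**Step 1. Where each kind of event goes.**

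| Route in protocol 10.3.1.4 | AE term | Symptomatic form | Row in the SAP 15.1.2 PT table |
|---|---|---|---|
| A. No symptoms, judged an AE | blood pressure decreased | No | 'Blood pressure decreased' |
| B. Symptoms, no other diagnosis | hypotension | Yes | 'Hypotension' |
| C. Symptoms, unifying diagnosis | that diagnosis | Yes | None, unless the diagnosis codes to a listed PT or the drop is also recorded separately under 10.3.1.2 |

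Routes B and C together make up symptomatic hypotension, and the form identifies both.

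**Step 2. What each visible output can show.**

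- PT table: separates A from B. It cannot identify most C events. To give an example of my own, a diagnosis of dehydration is not among the nine PTs.
- Orthostatic and diastolic hypotension rows: 10.3.1.4 does not mention these terms, so the row alone does not say whether symptoms were present.
- Profile of hypotension: its listed contents include no symptom status and no split by PT, so A and B are combined.
- Vital-sign tables (SAP 15.3): measured values only.
- General TEAE tables (SAP 15.1.1): contain C events under their diagnosis, but nothing links them to a blood-pressure drop.

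**Step 3. Size.** The planned arm is 55 subjects (SAP 4.5), so one subject is 1/55 = 1.8 percentage points. The documents give no event counts. Assume, in one arm, h = 3 subjects on route B, a = 5 with route A events only, and d = 0, 1 or 2 whose only symptomatic event is on route C and outside the nine PTs.

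- 'Hypotension' row: h/55 = 3/55 = 5.5%.
- Count from the form: (h + d)/55 = 3/55, 4/55 or 5/55 = 5.5%, 7.3% or 9.1%.
- Shortfall of the row: d/55 = 0, 1.8 or 3.6 points.
- Symptomatic share of subjects in the profile: h/(h + a) = 3/8 = 38%.
- With a = 0 the share is 3/3 = 100%; with a = 10 it is 3/13 = 23%.

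The shortfall depends only on d, and the mixing in the profile only on a relative to h. All three are assumptions.

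**The case against.** The strongest reply is that the SAP already separates the main groups. Events of interest are tabulated by PT and arm, and the protocol's own AE terms put asymptomatic drops and unexplained symptomatic drops on different rows. This stands. A reader might infer that the SAP reports one pooled hypotension incidence. It does not: no category total is specified, and only the profile clearly combines the terms.

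A reader might also infer that the SAP breaks the commitment in protocol 14.4. That goes too far. The sentence speaks of subjects who report these AEs, and if it means AE terms only, the 'Hypotension' row meets it.

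Next, a drop explained by another illness is a different event from unexplained hypotension, and leaving it out of the PT category is defensible. That also stands, and is why the fix keeps the two apart. Nor are such events lost, since they appear in the general TEAE tables.

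Asymptomatic predominance may not carry over from earlier studies. Here an asymptomatic drop becomes an AE only by clinical judgment, and protocol 9.12.6.9.1 schedules standing blood pressure only at Screening. That is a fair limit on how mixed the profile will be.

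The comparison with SAP 15.1.3 is not exact. That page recovers symptoms that collapse into one AE term, whereas the form here would count and classify events. It shows only that this SAP already uses a symptom page.

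CTCAE grade is at best a partial substitute. The general scale in protocol Table 10.2.3.2.1 puts asymptomatic events and mild symptoms together in Grade 1.

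Parts of SAP sections 15, 15.1.1 and 15.3 are redacted, and a listing could use the form. The claim is therefore limited to visible output.

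Finally, the SAP change log (section 22) records removal of events suggestive of hypotension. A reader might infer that a symptomatic count was dropped. The entry compares SAP versions and gives no reason, so it supports no such conclusion.

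**Conclusion.** The point holds as a minor reporting gap. The PT table gives probably most, possibly all, of the symptomatic percentage; with no counts in the documents, that is a judgment. Three things remain unavailable from the visible plan: a hypotension profile restricted to symptomatic events, the symptom status of the orthostatic and diastolic rows, and identification of symptomatic drops coded under another diagnosis.

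The number of subjects affected by the last is unknown and may be zero, at 1.8 points each with 55 per arm. The conclusion assumes that sites follow protocol 10.3.1.4 and that no redacted SAP text already uses the form. The safety analysis is descriptive: no confirmatory test is affected, and nothing here implies a bias between arms.

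**What to change.** Keep the PT table unchanged and make two additions to SAP 15.1.2.

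1. A supplementary table by arm giving n (%) and the exposure-adjusted rate for subjects with at least one symptomatic hypotension eCRF after first dose and within the SAP's 30-day post-treatment safety window. Use separate rows for AE terms inside and outside the nine PTs, so that drops explained by another diagnosis are not merged with unexplained ones.
2. A split of the 'Profile of hypotension' by whether the form was completed.

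Both use data already collected. The cost is one added table, one split table, and a footnote that some events appear in two tables.

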10. Have used any other investigational product or investigational medical device for the treatment of ACH or short stature at any time, including BMN 111.

B:OMARIN [®]	Study 111-301 Amendment 4	Page 55
------------------------------	---------------------------	---------

11. Current chronic therapy with antihypertensive medications, angiotensin-converting enzyme (ACE) inhibitors, angiotensin II receptor blockers, diuretics, beta-blockers, calcium-channel blockers, cardiac glycosides, systemic anticholinergic agents, GnRH agonists, any medication that may impair or enhance compensatory tachycardia, diuretics, or other drugs known to alter renal or tubular function (Table 9.3.2.1).
12. Have been treated with growth hormone, insulin-like growth factor 1 (IGF-1), or anabolic steroids in the previous 6 months or treatment greater than 6 months at any time.
13. Have had > 1 month treatment with oral corticosteroids (low-dose ongoing inhaled steroid for asthma, or intranasal steroids, are acceptable) in the previous 12 months.
14. Planned or expected to have limb-lengthening surgery during the study period. Subjects with previous limb-lengthening surgery may enroll if surgery occurred at least 18 months prior to screening and healing is complete without sequelae.
15. Planned or expected bone-related surgery (ie. surgery involving disruption of bone cortex, excluding tooth extraction), during the study period. Subjects with previous bone-related surgery may enroll if surgery occurred at least 6 months prior to screening and healing is complete without sequelae.
16. Have had a fracture of the long bones or spine within 6 months prior to screening.
17. Pregnant or breastfeeding at the Screening Visit or planning to become pregnant (self or partner) at any time during the study.
18. Have aspartate aminotransferase (AST) or alanine aminotransferase (ALT) at least $3 \times$ upper limits of normal (ULN) or total bilirubin at least $2 \times$ ULN (except for subjects with known history of Gilbert's disease).
19. History of severe untreated sleep apnea.
20. Have had new initiation of sleep apnea treatment (eg, continuous positive airway pressure [CPAP] or sleep apnea-mitigating surgery) in the previous 2 months prior to screening.
21. Have current malignancy, history of malignancy, or currently under work-up for suspected malignancy.
22. Have known hypersensitivity to BMN 111 or its excipients.

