10.3 Procedures for Recording Adverse Events

10.3.1 Recording Adverse Events on an eCRF

Investigators should use precise medical terminology when recording AEs or SAEs on an eCRF. Avoid colloquialisms and abbreviations.

Record only one diagnosis, sign, or symptom per event field on the AE eCRF (eg, nausea and vomiting should not be recorded in the same entry, but as 2 separate entries).

In order to classify AEs and diseases, preferred terms will be assigned by the Sponsor to the original terms entered on the eCRF, using Medical Dictionary for Regulatory Activities (MedDRA) terminology.

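### The SAP's heart rate change event list has no measured-value terms, so an adverse event coded as a raised or lowered heart rate would miss the heart-rate event-of-interest tables

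*SAP*

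**What the plan says.** SAP 15.1.2 builds each event of interest from a stated MedDRA definition. For heart rate change, the definition is a list of named preferred terms: "Atrial tachycardia, Postural orthostatic tachycardia syndrome, Rebound tachycardia, Sinus tachycardia, Supraventricular tachycardia, Tachycardia, Tachycardia paroxysmal, Ventricular tachycardia, Bradycardia". No high level term, standardized query or open-ended wording widens it. Two outputs draw on it: "Incidence and exposure-adjusted event rates of heart rate change events by PT" and "Profile of heart rate change events".

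The hypotension category in the same section is also a list of named terms. It begins with "Blood pressure ambulatory decreased, Blood pressure decreased, Blood pressure diastolic decreased, Blood pressure orthostatic decreased, Blood pressure systolic decreased" and ends with "Blood pressure systolic inspiratory decreased, Diastolic hypotension, Hypotension, Orthostatic hypotension".

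On recording, Protocol 10.3.1.4 covers blood pressure. Its rule begins "If an asymptomatic drop in blood pressure meets the protocol definition of AE per clinical judgment of the reporter" and tells the site to enter such an event as a blood pressure decrease, with hypotension or a unifying diagnosis kept for symptomatic drops. The Protocol has no matching rule for heart rate. On coding, Protocol 10.3.1 says that "preferred terms will be assigned by the Sponsor to the original terms entered on the eCRF", so the term the site writes determines which category the event can enter.

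**The concern.** The category's name promises any change in heart rate, but its list holds only tachycardia and bradycardia terms. The neighbouring hypotension list counts a finding and a diagnosis alike. Heart rate is measured at every time point at which blood pressure is measured (Protocol 9.12.6.9.1), so an abnormal value can come to light in the same way. If a site judges such a value to be an adverse event and records it as a finding, a program that follows the SAP will not place it in the heart rate category.

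What is at stake is the completeness of one safety grouping. The profile table reports highest grade, events per subject, time to first onset, duration, action taken and outcome. It would describe only the events that were worded as tachycardia or bradycardia.

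**Working it through.** The plan states no figure on this point, so the check is a count of terms and a search for any rule that would close the gap.

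**Count of terms (SAP 15.1.2)**

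- Hypotension: five blood pressure decrease terms in the opening run, plus one more (systolic inspiratory), make 6 measured-value terms. Diastolic hypotension, hypotension and orthostatic hypotension make 3 diagnoses. 6 + 3 = 9.
- Heart rate change: eight tachycardia terms (one of them a postural syndrome) and one bradycardia term. 8 + 1 = 9, of which 0 are measured-value terms.

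**Search for a rule that brings a finding into the heart rate category**

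- Protocol 10.3.1 assigns the preferred term from the site's wording.
- Protocol 10.3.1.1 asks for the diagnosis if known and otherwise the sign or symptom. It does not convert a heart rate finding to tachycardia or bradycardia.
- SAP 15.1.1 has the achondroplasia-related term list reviewed and updated before database lock. SAP 15.1.2 states no such step for heart rate.

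Nothing found closes the gap.

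**Where an unlisted heart rate event would still be seen**

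- SAP 15.1.1: the general tables by system organ class, preferred term and grade, with exposure-adjusted rates, by treatment group.
- SAP 15.3: pre-dose to post-dose heart rate, as descriptive statistics and mean plots by visit. The threshold and shift tables there are for blood pressure only.
- SAP 15.4: percentages of subjects with an ECG heart rate rise above 25% to over 100 beats/min, or a fall above 25% to under 50 beats/min. Protocol Table 9.1.1 schedules no ECG on Day 2, Day 3 or at Week 6, although vital signs are taken then.

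**What is produced only from this list**

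These are the profile table and any count that combines heart rate events across preferred terms.

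**Size**

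With n1 events coded to listed terms and n2 coded to heart rate findings, the category shows n1/(n1 + n2) of them. The documents give neither n1 nor n2, and any percentage would only reflect the ratio chosen.

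**The case against.** The case for leaving the list alone has four parts.

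- **The events are not hidden.** A heart rate finding appears in the general tables with the same incidence and rate statistics, and the event-of-interest incidence table is itself laid out by preferred term. This stands. A reader might infer that such events disappear from the report, but SAP 15.1.1 rules that out. The loss is confined to the heart-rate grouping and its profile.
- **The difference between the lists has a reason.** Protocol 10.3.1.4 tells sites to use a finding term for an asymptomatic pressure drop, so the hypotension list has to include one. Without such a rule for heart rate, a site may simply write tachycardia or bradycardia, and both are listed. This makes the omission understandable, but it does not stop a site from writing a finding.
- **Recording rules shrink the pool.** Protocol 10.3.1.2 generally attributes secondary events to their primary cause, and 10.3.1.4 sends the signs of symptomatic hypotension to a separate form. A fast heart rate that accompanies symptomatic hypotension would often not be an adverse event of its own. This also stands, but it does not cover a heart rate change reported alone.
- **The coding is assumed.** The documents do not show that MedDRA version 22 has separate heart rate finding terms. This is correct, and the term names must be checked there.

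A reader might also infer from the exclusion of "any medication that may impair or enhance compensatory tachycardia" in Protocol 9.3.2 that tachycardia is an expected effect of BMN 111, so that the undercount would fall mainly on that arm. The criterion restricts concomitant medication and does not say this. Protocol 7.5.2.2 names injection site reactions and hypotension as the risks identified in Phase 2. Neither document gives heart rate event counts by arm.

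**Conclusion.** The point holds in a limited form. As written, the heart rate change category excludes any adverse event coded to a measured rise or fall in heart rate, while the parallel hypotension category includes measured falls in pressure. The affected outputs are the heart-rate incidence and rate table and the profile table.

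The conclusion rests on two assumptions: that at least some sites will word a heart rate event as a finding, and that MedDRA codes it to its own preferred term. The SAP's separate entries for blood pressure decreased and hypotension support the second by analogy. The number of events lost and any imbalance between arms cannot be estimated. The severity is minor, because the grouping is descriptive and no hypothesis test depends on it.

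**What to change.** In SAP 15.1.2, add to the heart rate change list the MedDRA version 22 preferred terms for a measured increase and a measured decrease in heart rate, together with any further bradycardia terms confirmed in that version. Show increases and decreases separately, because the present list combines eight fast-rate terms with one slow-rate term. Freeze the list before unblinding. Coding is due before database lock (SAP 15.1) and the blind is kept until then (SAP 4.6.1), so the coded terms can be checked without knowledge of treatment. If the omission is intended, a sentence giving the reason would do instead. The cost is one line in the SAP and a small programming change, with no new data.
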